14 CLINICAL EVALUATIONS

Table 1 provides a summary of assessments to be conducted over the entire study.

14.1 ASSESSMENTS AT SCREENING/BASELINE

Prior to enrollment on the study, subjects will be screened to determine if they meet eligibility requirements. In addition, certain baseline assessments will be made that are part of eligibility determinations but also provide physiological, psychological, and disease status information prior to active treatment. Because the initial assessments are intensive, they have been separated into groups designated as screening and baseline assessments. The screening and baseline assessments should be conducted concurrently as scheduling permits.

14.1.1 Screening Assessments:

Screening assessments to be completed within 30 days of randomization (unless otherwise indicated) include:

- 1. Complete medical history and physical exam.
- 2. Psychiatric evaluation including assessment of adult ADD and SCID evaluation for DSM-IV diagnosis of cocaine dependence and Axis-I disorders.
- 3. ASI evaluation
- 4. HAM-D evaluation
- 5. Hematology
- 6. Blood chemistries
- 7. Routine urinalysis
- 8. Urine drug screen
- 9. Infectious disease panel
- 10. Rapid Plasma Reagin (RPR) test for syphilis
- 11. RAB
- 12. ECG
- 13. Pregnancy test (if female) within 2 days before study agent administration.
- 14. Blood sample as a control for assessments of selegiline/selegiline metabolite levels.

15. Prior medications. All medications taken by the subject for the 60 days prior to the first day that the subject receives study agents will be documented on a Prior Medication CRF. Data will be reviewed and recorded on the day that the subject first receives study agents but before study agent administration.

Assessment	Screening	Baseline										Termin-	Follow-
C4 1 XV. 1	(aamnlatad	within 30 days				1	1	1	1	1	1	ation ^a	up
Study Week		lomization)		1	2	3	4	5	6	7	8		12
Screening													
Informed Consent	Х												
SCID	Х												
Psychiatric	Х												
evaluation													
ADD	Х												
Medical History	Х												
Infectious disease	Х												
panel/RPR			-										
Safety			R										
Physical exam	Х		Α									Х	
Prior Medications	x ^b		N										
Vital Signs/weight		3 X/week for 2 weeks	D	3X	3X	Х	Х	Х	Х	Х	Х	Х	
Hematology	Х		Ο				Х					Х	
Blood Chemistry	Х		Μ				Х					Х	
Routine Urinalysis	Х		Ι				Х					Х	
12-lead ECG	Х		Ζ									Х	
Pregnancy test	(completed within 2 days before agent administration)		Α				X					Х	
Adverse Events			T	Х	Х	Х	Х	Х	Х	Х	Х	Х	Х
Con. Meds.			Ι	Х	Х	Х	Х	Х	Х	Х	Х	Х	
Efficacy			0										
HAM-D	X		Ν			Х		Х		Х		Х	
ASI	Х							Х				Х	
Urine BE/creatinine		3 X/week for 2 weeks		3 X	3 X	3 X	3 X	3 X	3 X	3 X	3 X	Х	Х
SUR		3 X/week for 2 weeks		3 X	3 X	3 X	3 X	3 X	3 X	3 X	3 X	Х	X ^c
Urine drug screen		3 X/week for 2 weeks		Х	Х	Х	Х	Х	Х	Х	Х	Х	
RAB	Х											Х	
BSCS		Weekly x 2 weeks		Х	X	Х	Х	Х	X	Х	Х	Х	
CGI-self		Weekly x 2 weeks		Х	Х	Х	Х	Х	X	Х	Х	Х	
CGI-observer		Weekly x 2 weeks		Х	Х	Х	Х	Х	Х	Х	Х	Х	
Treatment Compliance-Drugs				3 X	3 X	3 X	3 X	3 X	3 X	3 X	3 X	Х	
Treatment Compliance-Therapy			1	Х	X	Х	X	Х	X	Х	Х	Х	
Blood selegeline/ metabolites	х		1			X			x				

Table 1. Overview of Study Assessments During Screening and Double-Blind Treatment

^a At the termination study visit or if the subject discontinues prematurely. ^b Prior medications will be recorded on the date the subject signs the informed consent for the prior 60 days and will be updated on study day 1 before patch application.

^c SUR at follow-up is subject's report of use of cocaine, opiates, alcohol, nicotine, and marijuana in the last 30 days.

14.1.2 Baseline Assessments

Baseline assessments to be completed over a 14-day consecutive period within the screening period include the following:

- 1. Three-times weekly urine BE plus creatinine measurements for two weeks. Subjects must provide six urine specimens in a consecutive 14-day period, three of which must be positive for urine BE (> 300 ng/mL). Ideally 3 of the specimens will be obtained in one week and 3 in the next week. No more than 4 of the specimens may be obtained in a 7-day period of the 14-day baseline.
- 2. Three-times weekly urine drug screen.
- 3. Three-times weekly vital signs and weight collected during visits when urine specimens are provided.
- 4. The following must be obtained weekly for two weeks:
 - a. BSCS
 - b. CGI-S
 - c. CGI-O
- 5. SUR including cocaine, alcohol, nicotine, and marijuana must be obtained 3 times per week for two weeks, documenting daily self report of use for the two week period.

14.2 ASSESSMENTS DURING DOUBLE-BLIND TREATMENT

Over the 8-week period of active treatment, subjects will return to the clinic three times per week (ideally on Monday, Wednesday, and Friday). Assessments will be performed as follows:

At each visit:

- 1. SUR
- 2. Urine BE and creatinine
- 3. Vital signs (just the first two weeks then weekly thereafter)
- 4. Treatment compliance-drugs
- 5. Treatment compliance-therapy (at each session attended)

Once per week at the first visit each week:

- 1. Vital signs (after the first two weeks when vital signs are taken at each visit)
- 2. Urine drug screen
- 3. AEs
- 4. Concomitant medications
- 5. BSCS
- 6. CGI-S
- 7. CGI-O

At the first visit of weeks 3 and 6:

1. Blood for selegiline/selegiline metabolites

At the first visit of study week 4:

- 1. Hematology
- 2. Blood chemistries
- 3. Routine urinalysis
- 4. Pregnancy test (if female)

At the first visit of study weeks 3, 5, and 7

1. HAM-D

At the first visit of study week 5

1. ASI

14.3 ASSESSMENTS AT DOUBLE-BLIND STUDY TERMINATION

At the final scheduled study visit during the treatment phase of the study or if the subject discontinues prematurely, regardless of the reason (request that the subject return for final assessments), the following assessments will be performed:

- 1. If the subject discontinues prematurely, determine the reason for termination.
- 2. Physical exam
- 3. Vital signs
- 4. SUR
- 5. Urine BE and creatinine
- 6. AEs
- 7. Urine drug screen
- 8. BSCS
- 9. CGI-S
- 10. CGI-O
- 11. Hematology
- 12. Blood chemistries
- 13. Routine urinalysis
- 14. Pregnancy test (if female)
- 15. ASI
- 16. RAB
- 17. HAM-D
- 18. ECG
- 19. Treatment compliance
- 20. Concomitant medications

NOTE: Subjects that start the study on a Monday will finish the last day of the last week on a Sunday. The final assessments in these subjects will be on the next possible day after Sunday, preferably Monday. Any urine BE data collected after treatment day 56 will be used to score a day as a use or non-use day up to study day 54.

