16.2 OUTCOME MEASURES

16.2.1 Primary Outcome Measure

The basic outcome variable is the weekly proportion of cocaine non-use days. Cocaine use and non-use days will be defined by subject self-report of use, confirmed or disproved by quantification of urine BE. For the primary efficacy response, each day of the 8-week study will be coded as either a use or a non-use day based on the self-reports and on the urine BE data. Three urine collection days are scheduled per calendar week. The first day that the subject receives the investigational agent will not be scored as a use or non-use day.

Because of the pharmacokinetics of cocaine and BE, carryover from previous cocaine use may be difficult to distinguish in the laboratory from new use. The rules enunciated by Preston *et al.*¹⁷, modified to meet the conditions of this study, (Rules 1-5 below) will facilitate classification of each assessment day as use or no-use.

The following will indicate "new use":

RULE 0: Subject reports new use.

The subject self report claims no new use or SUR is missing but any of the following applies:

RULE 1:	An increase in cocaine metabolite concentration over concentration of preceding urine specimen to any value over 300 ng/ml.
RULE 2:	Both of the following occur: 1) cocaine metabolite concentration is greater than 300 ng/mL and 2) cocaine metabolite concentration is greater than one-half of the concentration measured in the preceding urine specimen.
RULE 3:	Cocaine metabolite is greater than 300 ng/ml in the first urine specimen collected in the study.
RULE 4:	If the previous urine specimen was collected more than 2 calendar days before, urine specimen with cocaine metabolite greater than 300 ng/ml.
RULE 5:	Creatinine less than 20 mg/dl and cocaine metabolite/creatinine ratio is increased compared to that of previous specimen. (Cocaine metabolite does not have to be above 300 ng/ml).

Assessment days may be less or more than 48 hours apart in this study. For this reason, the Preston rules were modified to delete reference to previous urine specimen collected at least 48 hours earlier.

Self-report gives preliminary determination of each day as a use or non-use day. Non-use days are confirmed or disproved by the urine BE data as follows:

- 1. Subject reports no new use since last urine BE or within the preceding 72 hours (whichever is the shorter time frame) but urine BE shows new use, then score the preceding day as a use day.

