16.4 ANALYSIS PLAN

Each of the primary and secondary efficacy outcome measures will be analyzed for the intent-totreat and for the evaluable population. Major differences in the results, if any, will be further explored. While there is every intent to be complete in describing the analyses to be performed, it is not possible to anticipate every contingency and some adjustments may be required to meet constraints posed by the structure of the data.

All statistical tests will be two-sided at a 5% level of alpha. Confidence intervals will be two-sided with a 95% confidence coefficient.

Primary Efficacy Outcome

The primary outcome variable for each subject is the weekly proportion of cocaine non-use days. Each subject's weekly proportion is equal to the number of his/her cocaine non-use days divided by the number of his/her non-missing study days during that week (a maximum of 6 days for week 1 and 7 days for weeks 2 through 8).

The weekly mean proportion of cocaine non-use days on study will be compared between treatment groups using Generalized Estimating Equations (GEE). GEE provide a model-based regression methodology applicable for the analysis of the correlated data that will result from this repeated measures longitudinal study.

The GEE procedure proposed by Liang and Zeger¹⁸ and Zeger and Liang¹⁹ (Biometrics, 1986) model the population average and has several useful features:

- 1. It can be used to analyze different types of outcomes such as continuous, binary, or count.
- 2. It can be used to analyze an unbalanced design caused by either differing numbers of observations per person or by observations taken at different times.
- *3.* The parameter estimates are consistent even if assumptions about the variance structure are not completely accurate.

Secondary Efficacy Outcomes

As a secondary analysis, the baseline proportion of cocaine non-use days, site, gender, diagnosis of ADD, severity of depression during screening, and their first-order interactions with treatment will also be included in the model. Presentation will include the full model with all terms and a reduced model containing only significant terms.

Unless the primary response analysis implies the need for a more elaborate model, between group comparisons of the secondary outcomes will be performed as follows:

- 1. Proportion of successful subjects, measures A, B, and C, will be assessed by Chi-square tests.

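### The Section 14.3 note, read literally, stops the final (day 57) urine from overruling day 56, a day that the primary endpoint scores

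*Protocol*

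**What the plan says.** The note in Protocol Section 14.3 deals with subjects whose eighth week ends on a weekend. "Subjects that start the study on a Monday will finish the last day of the last week on a Sunday". For the closing visit it says: "The final assessments in these subjects will be on the next possible day after Sunday, preferably Monday". It then says that any BE result from a specimen given later than day 56 of treatment "will be used to score a day as a use or non-use day up to study day 54".

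Section 16.2.1 defines the endpoint data: "each day of the 8-week study will be coded as either a use or a non-use day". There is one exception: "The first day that the subject receives the investigational agent will not be scored as a use or non-use day". Criterion 1 of that section covers a subject who reports no new use over the interval since the last urine or the past 72 hours, whichever is shorter. If the "urine BE shows new use, then score the preceding day as a use day". Criterion 2 treats self-reported non-use as missing when no urine BE assessment follows within 7 days, or when the subject's concordance rate is below 70%. Criterion 3 accepts every self-report of use.

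Section 16.4 sets the denominator of the weekly proportion: "a maximum of 6 days for week 1 and 7 days for weeks 2 through 8".

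**The concern.** Day 56 is in the primary endpoint, and for a Monday starter the day-57 urine is the only specimen that can overrule a report of non-use on it. The note appears to forbid this. The endpoint is meant to be self-report confirmed or disproved by urine. Under the literal note, the last treatment day keeps the subject's own account even when the next morning's urine contradicts it. A programmer who follows Section 14.3 and one who follows Section 16.2.1 would produce different week 8 values from the same data.

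**Working it through.** This is a day count and does not depend on alpha, power, standard deviation or sample size.

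**Scored days.** Section 16.4 gives 6 + 7 × 7 = 55. Section 16.2.1 excludes only day 1, so the scored days are 2 to 56, which is also 55. Days 55 and 56 are therefore in the endpoint.

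**Calendar for a Monday starter, with Monday/Wednesday/Friday visits (Section 14.2).** Day 1 is a Monday, so day 1 + 7 × 7 = 50 is a Monday. The last on-treatment visits fall on days 50, 52 and 54 (Friday). Day 56 is the Sunday, as the note says, and the preferred final visit is Monday, day 57.

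**Criterion 1 applied to the last urines.**

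| Urine on | Day it can overrule | Interval it looks back over |
|---|---|---|
| Day 54 | 53 | back to the day-52 urine |
| Day 57 | 56 | days 54, 55 and 56 (last urine and 72 hours coincide) |

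The day-57 urine can overrule day 56 and no other day. Saturday, day 55, cannot be overruled under either wording, because a Monday urine always points to the Sunday.

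**What the literal note changes.** The overruling of day 56 is lost: 1/55 = 1.8% of scored days and 1/7 = 14% of week 8.

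**Worked case.** A subject reports no use in week 8, no on-treatment urine contradicts this, concordance is at least 70%, and the day-57 urine shows new use. Section 16.2.1 scores day 56 as a use day, giving 6/7 = 86%. The note leaves it as non-use, giving 7/7 = 100%.

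**Other start days on the same visit pattern.** The note's last sentence speaks of any urine after day 56, so it is not confined to Monday starters.

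- Wednesday and Friday starters: the last on-treatment urine is on day 55 (overrules day 54). If a urine is then taken at the next pattern visit, day 57, it points to day 56 and is blocked in the same way.
- Tuesday and Thursday starters: the last on-treatment urine is on day 56 (overrules day 55). The next pattern visit is day 58, which points to day 57, outside the scored period. The note changes no overruling for them.

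**Criterion 2.** The day-57 urine comes 2 days after day 55 and 1 day after day 56, so it meets the 7-day requirement for both.

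**The case against.** The best defence is that the note was never meant as an upper limit. Day 57 minus 72 hours is day 54, which is the look-back of criterion 1. If the sentence means that the urine reaches back as far as day 54, nothing conflicts. Day 54 could also be a slip for day 56. Section 16.2.1 refers to scoring examples in Appendix VI, which is not in the text at hand and might settle the intent. These points lower confidence, but the wording does not state either reading, and a sentence that needs such a reading should be corrected.

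It can also be said that the assignment to day 56 is conditional. This is true: the note prefers Monday but allows a later visit, and a day-58 urine points outside the scored period. The effect is also small, falls at the end of week 8 only, and applies by the same rule in both blinded arms.

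A reader might infer something stronger: that both days of the last weekend (2/55 = 3.6%; 2/7 = 29% of week 8) lose all urine verification, or become missing when non-use is reported. That would follow only if the barred urine also failed to count as the following assessment under criterion 2. Criterion 2 asks for a urine BE assessment within 7 days. It does not require that this urine be allowed to score the day.

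A reader might also infer that the note directs the urine to a day already checked by its own specimen. It does not, because the day-54 urine overrules day 53, while day 54 lies in the look-back of the day-57 urine.

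**Conclusion.** The point holds in limited form, with medium confidence. Read literally, the Section 14.3 note conflicts with Sections 16.2.1 and 16.4, because it stops a day-57 urine from overruling day 56. The direct effect is one day per affected subject: 1 of 55 scored days (1.8%), or 1 of 7 in week 8 (14%). It arises only when the subject reports non-use and the day-57 urine shows new use. One non-concordant day would also leave that subject's concordance calculation, which matters only near the 70% threshold.

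This rests on the Monday/Wednesday/Friday pattern, a final urine on day 57, and the literal sense of the note. The documents show no bias between arms, and they do not support a loss of all urine confirmation for days 55 and 56.

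**What to change.** In the Section 14.3 note, replace study day 54 with study day 56 as the last day that post-treatment urine may score. Cross-refer to Section 16.2.1, so that its preceding-day rule and its 7-day confirmation window apply unchanged. Add that a discordant urine whose preceding day falls after day 56 does not overrule a treatment day.

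Do not add a rule that assigns any discordant urine within 72 hours of day 56 to day 56. A urine on day 58 or 59 has day 57 or 58 as its preceding day, so such a rule would contradict Section 16.2.1 and could place post-treatment use on a treatment day.

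Check that the scoring examples in Appendix VI agree with the corrected sentence, and settle the wording before unblinding, because it defines primary endpoint data. The cost is a short change to one note and the matching line in the scoring program. The specimen is already collected.

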14.4 ASSESSMENTS AT FINAL FOLLOW-UP

Final off-treatment assessments will be performed four weeks after the 8 week period of doubleblind treatment and include:

- 1. Questions regarding amount of cocaine/other substance used over the last 4 weeks, current treatment for drug or alcohol abuse, and an impression of the study medication.
- 2. Urine BE and creatinine
- 3. AEs

14.5 ASSESSMENTS IN THE EVENT OF DEATH ON STUDY

In the event a subject dies while on study, the site investigator is responsible for informing the local medical examiner's office of this protocol, and of the procedures to be followed for collecting specimens and information required for study-related toxicological analyses. The site investigator may also refer the medical examiner directly to the Center for Human Toxicology [contact]) for additional information. The following specimens will be collected:

- 10 ml of whole blood in non-fluoride tube (red top).
- 10 ml of whole blood in a fluoride tube (grey top).
- 10 ml of urine.
- 20 gm of liver tissue.

NOTE: If whole blood cannot be obtained then blood is to be collected from body fluids in the thoracic cavity.

Subjects will be asked to consent to allow the site investigator to request the following in the event of their death while participating in the study: 1) samples of certain bodily fluids and tissues taken for the purposes of this study only, and 2) an autopsy. The consent for these is not mandatory for subject's participation in the study.

14.6 ASSESSMENT METHODS

14.6.1 Vital Signs

Vital signs to be assessed include oral temperature, sitting blood pressure, pulse rate, respiratory rate, and standing blood pressure and pulse rate (standing 1 minute), and standing blood pressure and pulse rate (standing 3 minutes). More frequent monitoring of vital signs may be obtained at the investigator's discretion.

14.6.2 Hematology

Blood will be collected in anticoagulant containing vacutainer tubes for hematologic assessments. Complete blood counts (CBC) with differentials and platelet count will be performed. Quantitative analyses for hemoglobin, hematocrit, red blood cells, platelets, total white blood cells, and percentage of neutrophils, lymphocytes, monocytes, eosinophils, and basophils will be performed. Analyses will be performed in the institutions clinical laboratory. Laboratories performing these assessments should be either directly regulated by the College of American Pathologist (CAP) or the Clinical Laboratory Improvement Act of 1988 (CLIA) or indirectly according to CLIA guidelines.

14.6.3 Blood Chemistries

Blood will be collected in non-anticoagulant containing vacutainer tubes and serum separated according to standard procedures. Quantitative analysis will be performed for the following analytes: sodium, potassium, chloride, carbon dioxide, glucose, creatinine, albumin, total protein, calcium, cholesterol, triglycerides, alanine aminotransferase (ALT/SGPT), aspartate aminotransferase (AST/SGOT), gamma glutamyltranspeptidase (GGT), total bilirubin, lactic dehydrogenase (LDH), alkaline phosphatase (ALP), blood urea nitrogen (BUN), and uric acid. Laboratories performing these assessments should be either directly regulated by CAP or CLIA or indirectly according to CLIA guidelines.

14.6.4 Routine Urinalysis

Urine will be collected by clean catch and analyzed for specific gravity, pH, glucose, protein, ketones, occult blood, white blood cells, red blood cells, and epithelial cells. Laboratories performing these assessments should be either directly regulated by CAP or CLIA or indirectly according to CLIA guidelines.

14.6.5 Infectious Disease Panel/RPR

Blood will be collected in a non-anticoagulant containing vacutainer tube and serum separated according to standard procedures. Qualitative analysis reporting positive/negative results will be performed for the following analytes: Hepatitis B surface antigen, Hepatitis B surface antibody, Hepatitis B core antibody, and Hepatitis C virus antibody. A purified protein derivative (PPD) skin test for tuberculosis will be performed and if positive a chest x-ray is required to assess active tuberculosis. A rapid plasma reagin test (RPR) for syphilis will be performed. If the RPR test is positive, a FTA-abs, MHA-TP, or TP-PA confirmatory test for active syphilis will be performed. If either confirmatory test is positive, the subject will be referred for treatment and will be considered eligible only after proof of completion of treatment is provided.

14.6.6 Pregnancy Test

Pregnancy tests designed to measure human chorionic gonodotropin will be used. All female subjects will be tested regardless of their child-bearing capacity.

14.6.7 HAM-D

The HAM-D¹³ is a 24-item interviewer administered assessment of the subject's level of depression. The HAM-D will be administered by an experienced staff member with clinical experience in diagnosing psychiatric patients as well as experience with administering the HAM-D.

14.6.8 ADD Assessment

An assessment from the DSM-IV criteria for childhood ADHD has been adapted to diagnose adult ADD. This interview assesses the subject's inattention, hyperactivity, and impulsivity both as the childhood history and as current adult behaviors. The ADD assessment will be administered by a staff member with clinical experience in assessing subjects with ADD.

